14.2 Analysis of Secondary Endpoints

Secondary endpoints in this clinical trial will: (a) assess the induction of IFN- γ T-cell response to the total peptide pool, and (b) estimate the proportion of patients alive without disease progression at two years after resection. Analyses of these secondary endpoints will be based on the 15 patients treated at the recommended vaccine dose.

The induction of IFN- γ T-cell response will be based on ELISPOT assessments taken prior to vaccine administration and at week 16. The proportion of patients who achieve more than 55 SFU/ 10^6 PBMC *or* 3 times their baseline level will be presented with a 90% exact binomial confidence interval. Based on a cohort of size 15, the confidence interval will be no wider than 0.46.

The proportion of patients alive, without disease progression at two years after resection will be estimated using the method of Kaplan-Meier. The endpoint will be calculated as the time between pathological confirmation of complete resection and the first of disease recurrence or death. Patients who are disease-free at the time of study reporting will have their follow-up censored at the time of the last study visit. Patients who were disease-free at the time of their last assessment and who have either been lost to follow-up or withdrawn consent will have their follow-up censored at the time of the last study assessment. The proportion of patients alive and disease-free at two years will be presented with 90% confidence intervals estimated using log(-log(DFS)) methodology.

14.3 Analysis of Correlative Endpoints

Longitudinal analyses of PBMC immune response kinetics to the peptide pool will be presented graphically and descriptively at each time point. Changes in the magnitude of the response relative to pre-treatment at several different time points after vaccination will be summarized descriptively. Changes in response between pre-treatment and 16 weeks post-vaccination, which is the time of the primary immunologic endpoint, will be assessed using the Wilcoxon signed-rank test.

CONFIDENTIAL

This document is confidential. Do not disclose or use except as authorized.

Immune studies of T cell subpopulations (CD4⁺, CD8⁺, central/effector memory cells, Th1/Th2 cells, Tregs, etc.), myeloid-derived suppressor cells (MDSC), CTL response, and T cell activation status will be summarized using descriptive statistics.

14.4 Analysis of Safety and Toxicity Data

Analysis set and grouping for the analyses: All patients who receive one or more doses of NeoVax will be included in the safety analysis. All listings and tables will be presented by dose level.

Adverse events (AEs): All adverse events recorded during the study will be summarized. The incidence of treatment emergent adverse events will be summarized by dose level according to primary system organ class, severity based on the National Cancer Institute's Common Terminology Criteria for Adverse Events (CTCAE) version 4.0, type of adverse event, and relationship to the vaccine. Deaths reportable as SAEs and non-fatal serious adverse events will be listed by patient and tabulated by primary system organ class, type of adverse event, and dose level.

DLTs will be listed and their incidence summarized by primary system organ class, worst grade based on the CTCAE version 4.0, type of adverse event, and by dose level. Any other information collected (e.g. start/end dates and duration of adverse event, severity or relatedness to study medication) will be listed, as appropriate.

Laboratory abnormalities: All laboratory values will be converted into SI units, as appropriate, and the severity grade calculated using CTCAE, version 4.0. Parameters for which a grading does not exist will be classified into low/normal/high group by means of laboratory normal ranges. For each laboratory test (e.g., hematology, biochemistry) a listing of laboratory values will be provided by laboratory parameter, patient and treatment group. The frequency of notable lab abnormalities (i.e., newly occurring CTCAE grade-3 or -4 laboratory toxicities), will be displayed by parameter, cycle, and dose level. Similarly, the frequency of all laboratory abnormalities will be displayed by parameter, worst CTCAE version 4.0 grade experienced and dose level. A separate listing will display notable laboratory abnormalities (i.e., newly occurring CTCAE grade-3 or -4 laboratory toxicities). Laboratory data will be summarized by presenting grade shift tables for those parameters for which CTCAE version 4.0 allows classification. All remaining data will be summarized by presenting shift tables based on normal ranges.

Laboratory data will be also be displayed by presenting summary statistics of raw data and change from baseline values (means, medians, standard deviations, ranges).

CONFIDENTIAL

15 PUBLICATION PLAN

This study is intended for publication, even if terminated prematurely. Publication may include any or all of the following: posting of a synopsis online, abstract and/or presentation at a scientific conference, or publication of a full manuscript. The Sponsor will work with the Principal Investigator and authors to submit a manuscript describing study results within 24 months after the last data become available; which for vaccine trials, may take up to several months after the last patient visit.

CONFIDENTIAL

This document is confidential. Do not disclose or use except as authorized.

This document is confidential. Do not disclose or use except as authorized.

DANA-FARBER CANCER INSTITUTE
Nursing Protocol Education Sheet

Protocol Number:	13-240
Protocol Name:	Ph I Study with Personalized NeoAntigen Cancer Vaccine in Melanoma
DFCI Site PI:	[name]
DFCI Research Nurse:	; [name]; [name]; [name]

Page the DFCI research nurse or DFCI site PI if there are any questions/concerns about the protocol.

*Please also refer to **ONC 15: Oncology Nursing Protocol Education Policy***

This is a PI Initiated Study & Therefore There is No Alert Page

SPECIAL NURSING CONSIDERATIONS UNIQUE TO THIS PROTOCOL

Study Design	This personalized NeoAntigen Cancer Vaccine approach has not been done in humans before. The vaccine is a tumor antigen and will hopefully induce immune responses against tumor cells that are much stronger than what has previously been achieved with traditional tumor vaccine approaches. The anticipated strong Immune responses should allow for clinical benefit. Please refer to Section 1.1 One Cycle = 22 Days (Section 5.4.1)
Dose Calc	***Please refer to Section 5.2.4
Study Drug Administration	
***Agent Administration Guidelines are found in Sections 5.3, 5.2.3.1, 5.2.3.2, 5.3.1, 5.2.4, & 7.1.8
 
Priming Doses: NeoVax (peptides + poly-ICLC)
 
 • Laboratory parameters must be reviewed and must re-meet Eligibility Criteria. (Section 5.2.3.1) • Subsequent treatment days, Laboratory parameters must continue to re-meet Eligibility Criteria. (Section 5.2.3.2) • 4 syringes containing 1 ml each of mixture for Neovax A, B, C, &D will be prepared for sub cu injections. • Administered Days 1, 4, 8, 15, & 22 via sub cu injections into 4 different anatomic sites. • Each of the 4 NeoVax syringes will be assigned to one of four extremities. (Example; NeoVax A will be injected into left arm on day 1, 4, 8 etc., NeoVax B will be injected into right arm on days 1, 4, 8, etc.) • NeoVax may be administered within 1 day of the scheduled administration date for days 4 & 8, within 3 days of the scheduled administration date for days 15 & 22 and 7 days for days 78 & 134 (Section 5.3.2) • For EACH clinic visit Participants are to be observed in the clinic for at least 60 minutes after the last of the 4 injections. (Section 5.3.3) • At EACH clinic visit Vital Signs are to be checked once between 30 and 90 minutes after the last injection for each clinic visit. (Section 5.3.3) 
Boost Phase:
 
 • NeoVax will be administered on Days 78 (week 12) and-134 (week 20) (Section 5.4.3)
Dose Mod & Tox	
Dose Modifications/Dosing Delay for Toxicity are outlined in Section 6.0, 6.3
 
 • DLT observation period is 7 weeks. (Section 5.4.4) • Toxicities will be graded using the NCI CTCAE version 4.0 (Section 5.5) • Maximum delay of NeoVax vaccine is 14 days. (Section 6.3.1) • Maximum number of times NeoVax may be delayed is 2. (Section 6.3.1)
Concom Meds	
***Concomitant Therapy Guidelines are in Section 5.6
 
 • Participants who have developed flu-like symptoms that were controlled with acetaminophen or non-steroidal anti-inflammatory drugs during previous treatments, Per Investigator's discretion, may be pre-treated with acetaminophen or NSAID. (Sections 5.2.3.2 & 6.2.3)

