5.3 Administration

Treatment Description					
Agent	Treatment phase	Schedule	Premedications Precautions	Dose	Route
NeoVax (peptides + poly-ICLC)	Prime	Days 1, 4, 8, 15, 22*	None	Poly-ICLC: 4 x 0.5 mg (total dose 2 mg) Peptides: 4 x 300 μ g per peptide Vol = 4 x 1 ml	injections into 4 different anatomic sites (0.5 ml i.d. & 0.5 ml s.c.)
NeoVax (peptides + poly -ICLC)	Boost	Days 78 and 134**	None	Poly-ICLC: 4 x 0.5 mg (total dose 2 mg) Peptides: 4 x 300 μ g per peptide Vol = 4 x 1 ml	injections into 4 different anatomic sites (0.5 ml i.d. & 0.5 ml s.c.)

* \pm 3 day treatment window is allowed except for days 4 and 8 (\pm 1 day)

** \pm 7 day treatment window is allowed

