5.3.1 Injections

Each of the up to 4 NeoVax syringes will be assigned to one of four extremities. At each immunization, each NeoVax syringe will be administered to the assigned extremity as follows: using one syringe/needle per site, 0.5 mL will be administered intradermally (i.d.) and 0.5 mL will be administered subcutaneously (s.c.) using the same syringe/needle at the same injection site (i.e. NeoVax A will be injected i.d. and s.c. into left arm on day 1, 4, 8 etc., NeoVax B will be injected i.d. and s.c. into right arm on days 1, 4, 8 etc.). Alternative anatomical locations for patients who are status post complete axillary or inguinal lymph node dissection or other contraindications that prevent injections to a particular extremity are the left and right midriff, respectively.

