5.4 Dose schema and staggering of patients

5.4.1 DLT and expansion cohorts

Five patients will be entered for the initial safety evaluation (Cohort 1). If two or more patients in Cohort 1 experience dose limiting toxicity (DLT) during the first 7 weeks of treatment, then that cohort will be determined to have unacceptable toxicity; otherwise, an additional 10 patients will be treated at the initial dose to increase the likelihood of detecting serious toxicities, to complete biologic correlative endpoints, and to gain preliminary experience with clinical tumor activity. If Cohort 1 is found to have unacceptable toxicity, then 5 patients may be enrolled on cohort -1 shown below. For Cohort -1, the dose of poly-ICLC is dropped by 50% relative to Cohort 1 but the dose of peptides remains the same. If two or more patients in Cohort -1 experience a DLT, then the study will be stopped. If none or only one patient experiences a DLT on Cohort -1, then 10 additional patients will be enrolled for additional toxicity evaluation, to complete biologic correlative endpoint, and to gain preliminary experience with clinical tumor activity. If four or more patients in the expansion cohort experience dose limiting toxicity (DLT) during the first 7 weeks of treatment, then that cohort will be determined to have unacceptable toxicity and further dosing of all patients will be stopped.

Dose De-escalation Schedule 1 cycle = 22days		
	Dose Level	Dose of poly-ICLC
	- 1	0.25 mg per injection site (4 injections, total dose 1 mg Vol = 4 x 0.875 ml)
Starting Dose →	1	0.5 mg per injection site (4 injections, total dose 2 mg)

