7.1.8 Administration

Following mixing with personalized neoantigen peptides, the vaccine (peptide + poly-ICLC) will be administered as follows: using one syringe/needle per site 0.5 mL will be administered intradermally and 0.5 mL will be administered subcutaneously.

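### The nursing sheet gives the priming injections as subcutaneous only, whereas the protocol splits every injection between intradermal and subcutaneous

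*Combined protocol and SAP*

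**What the plan says.** Four places in the protocol body give the route, and they agree.

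- The treatment table in Section 5.3, in both the prime and the boost row, specifies "injections into 4 different anatomic sites (0.5 ml i.d. & 0.5 ml s.c".
- Section 5.3.1 states that "0.5 mL will be administered intradermally (i.d.) and 0.5 mL will be administered subcutaneously (s.c.) using the same syringe/needle at the same injection site".
- Section 7.1.8 says "0.5 mL will be administered intradermally and 0.5 mL will be administered subcutaneously", with one syringe and needle per site. Section 7.2.8 repeats this.

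The Nursing Protocol Education Sheet, which follows the appendices, differs. Under the priming doses in its study drug administration row, one bullet says "4 syringes containing 1 ml each of mixture for Neovax A, B, C, &D will be prepared for sub cu injections" and the next says "Administered Days 1, 4, 8, 15, & 22 via sub cu injections into 4 different anatomic sites". The visible sheet does not mention the intradermal route at all. Its example of assigning syringes to limbs follows the example in Section 5.3.1 but leaves out the two routes. The boost bullet names no route.

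The row opens with a pointer: "Guidelines are found in Sections 5.3, 5.2.3.1, 5.2.3.2, 5.3.1, 5.2.4, & 7.1.8". Three of the sections listed there (5.3, 5.3.1 and 7.1.8) carry the split route.

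**The concern.** The sheet is written for the staff who give the injections. Its two priming bullets name one route where the protocol requires two, and nothing else in the sheet would expose the discrepancy. The syringe volume, number of sites and visit days all match the starting-dose regimen, so a fully subcutaneous injection would look correct on dose and volume.

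The bullets also cover the doses that carry most of the trial's information. As scheduled, all doses inside the 49-day DLT window of Section 5.5 are priming doses, because the first boost is on day 78. Five of the six doses given before the week-16 primary immunological endpoint (Section 8.1) are priming doses. Injection-site reactions are expected (Section 6.1.1), and the DLT definition in Section 14.1 deals with them specifically. What is at stake is therefore fidelity of the intervention: whether the safety and immune-response data describe the route that the protocol specifies.

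**Working it through.** The plan gives no figure to reproduce here. The check is a comparison of texts, followed by arithmetic on the stated volumes.

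**Comparison of the route**

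| Place | Route stated |
|---|---|
| Section 5.3 table, prime and boost | i.d. and s.c., 0.5 mL each per site |
| Section 5.3.1 | i.d. and s.c., 0.5 mL each, same needle, same site |
| Sections 7.1.8 and 7.2.8 | i.d. and s.c., 0.5 mL each, one needle per site |
| Nursing sheet, syringe preparation bullet | s.c. only |
| Nursing sheet, priming administration bullet | s.c. only |
| Nursing sheet, boost bullet | none stated |

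Only Section 5.3.1 says in terms that both halves go into the same site; the other sections give the split per site. Both versions stand in the current combined document, so neither blacked-out text nor a superseded amendment explains the conflict.

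**Volumes at the starting dose**

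Inputs: 1 mL per syringe (Section 5.3 and the sheet); a 0.5 + 0.5 mL split (Section 5.3.1); five priming visits, on days 1, 4, 8, 15 and 22 (Section 5.3). The number of syringes is *k*. The sheet says four; Section 5.3.1 says "Each of the up to 4 NeoVax syringes will be assigned to one of four extremities", so four is a maximum.

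- Protocol, per visit: i.d. = 0.5*k* mL and s.c. = 0.5*k* mL. For *k* = 4 this is 2 + 2 = 4 mL, which agrees with the table's total of four 1 mL injections.
- Sheet read literally, per visit: i.d. = 0 mL and s.c. = 1.0*k* mL.
- Volume moved per visit: 0.5*k* / 1.0*k* = 50% for every *k*.
- Over five visits: 5 × 0.5*k* = 2.5*k* mL moved out of 5*k* mL, with 5*k* intradermal deposits omitted.

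| Syringes (*k*) | Volume moved over 5 visits | i.d. deposits omitted |
|---|---|---|
| 1 | 2.5 of 5 mL | 5 |
| 2 | 5 of 10 mL | 10 |
| 3 | 7.5 of 15 mL | 15 |
| 4 (maximum, and the sheet's own count) | 10 of 20 mL | 20 |

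The rows below four are an assumption. The text on peptide pools and on the dosage form (Sections 5.2.2 and 5.2.4) is not legible in the public version. Section 14.1 rules out treatment only at three or fewer actionable peptides, so a patient with four could be treated, and fewer than four syringes is possible.

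Boost visits are left out because the sheet states no route for them. Dose level −1 is left out because Section 5.4.1 gives it as "0.25 mg per injection site (4 injections, total dose 1 mg Vol = 4 x 0.875 ml", and 0.5 + 0.5 = 1.0 mL exceeds 0.875 mL, so the body's split cannot be applied there unchanged.

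**The case against.** The best argument against giving this weight is that the protocol itself is not ambiguous. Its four statements of route agree, and the discrepancy sits in an appended sheet whose administration row begins by sending staff to the correct sections and whose first page tells them to page the research nurse or site investigator with questions. An error would need a nurse to pass over that pointer. Subcutaneous is also one of the two required routes, so the bullets omit something rather than name a forbidden route. The documents do not say that giving the intradermal half subcutaneously would change safety or immunogenicity.

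Most of this is fair, and it limits the size of the point. The pointer lowers the risk. The accurate description is that the bullets omit the intradermal half. There is no evidence of misadministration, and how likely staff are to be misled cannot be judged from the visible text. But the pointer does not correct the bullets: they read as a complete instruction, carry no section reference of their own, and give the reader no reason to look further.

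It can also be objected that a purely literal reading of the sheet yields only the four-syringe case. That is correct. The smaller counts apply to a patient for whom fewer syringes are prepared, and the 50% share does not depend on the count.

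Finally, referring the bullets to Sections 5.3 and 5.3.1 does not settle how 0.875 mL is split at dose level −1. That is true, but it is a separate gap in the protocol body, which this correction neither creates nor worsens.

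**Conclusion.** The concern holds. Two priming bullets contradict Sections 5.3, 5.3.1, 7.1.8 and 7.2.8 on the route. Followed as written at the starting dose, they would omit the intradermal half of every priming dose. The volumes rest on 1 mL per syringe, at most four syringes, and literal adherence to the bullets. Total dose is unchanged, and no endpoint definition, sample size, error rate or analysis is affected. This is a fidelity error that should be corrected because the sheet is addressed to the people who inject; it does not cast doubt on the design.

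**What to change.** In both priming bullets, replace the subcutaneous-only wording with: *i.d. and s.c. injections, split per syringe at the same site as specified in Sections 5.3 and 5.3.1*. Do not write 0.5 mL into the sheet, since that volume does not fit dose level −1. The boost bullet needs no change.

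The cost is an edit to two bullets on one education sheet, with no added patients, procedures or data items.
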